5.4.2 Exclusion Criteria

Exclusionary Diagnosis

1. Patients who have:
 - a) any other histological type of lymphoma including primary mediastinal (thymic) large B-cell (PMBL) or Burkitt lymphoma
 - b) primary refractory DLBCL (see [Section 5.1.1](#) for definitions)
 - c) a history of "double/triple hit" genetics DLBCL characterised by simultaneous detection of MYC with BCL-2 and/or BCL-6 translocation(s) defined by fluorescence *in situ* hybridisation. MYC, BCL-2, BCL-6 testing prior to study enrolment is not required

Exclusionary Previous and Current Treatment

2. Patients who have, within the 14 days prior to Day 1 dosing:
 - a) not discontinued CD20-targeted therapy, chemotherapy, radiotherapy, investigational anticancer therapy or other lymphomaspecific- therapy
 - b) undergone major surgery or suffered from significant traumatic injury
 - c) received live vaccines (see [Section 6.7](#) for details)
 - d) required parenteral antimicrobial therapy for active, intercurrent infections
3. Patients who:
 - a) have, in the opinion of the investigator, not recovered sufficiently from the adverse toxic effects of prior therapies
 - b) were previously treated with CD19-targeted therapy or IMiDs® (e.g., thalidomide, LEN)
 - c) have a history of hypersensitivity to compounds of similar biological or chemical composition to MOR00208, IMiDs® and/or the excipients contained in the study drug formulations
 - d) have undergone ASCT within the period ≤ 3 months prior to the signing of the informed consent form. Patients who have a more distant history of ASCT must exhibit full haematological recovery before enrolment into the study
 - e) have undergone previous allogenic stem cell transplantation
 - f) have a history of deep venous thrombosis/embolism, threatening thromboembolism or known thrombophilia or are at a high risk for a thromboembolic event in the opinion of the investigator and who are not willing/able to take venous thromboembolic event prophylaxis during the entire treatment period
 - g) concurrently use other anticancer or experimental treatments

Exclusionary Patient's Medical History

4. Prior history of malignancies other than DLBCL, unless the patient has been free of the disease for ≥ 5 years prior to screening. Exceptions to the ≥ 5 year time limit include history of the following:
 - a) basal cell carcinoma of the skin
 - b) squamous cell carcinoma of the skin
 - c) carcinoma *in situ* of the cervix
 - d) carcinoma *in situ* of the breast
 - e) carcinoma *in situ* of the bladder
 - f) incidental histological finding of prostate cancer (Tumour/Node/Metastasis [TNM] stage of T1a or T1b)
5. Patients with:
 - a) positive hepatitis B and/or C serology (see [Section 7.2.13.2](#) for details)
 - b) known seropositivity for or history of active viral infection with human immunodeficiency virus (HIV)
 - c) CNS lymphoma involvement – present or past medical history
 - d) history or evidence of clinically significant cardiovascular, CNS and/or other systemic disease that would in the investigator's opinion preclude participation in the study or compromise the patient's ability to give informed consent
 - e) history or evidence of rare hereditary problems of galactose intolerance, the Lapp lactase deficiency or glucose-galactose malabsorption
 - f) gastrointestinal abnormalities including the inability to take oral medication, requiring intravenous alimentation, or prior surgical procedure affecting absorption
 - g) history or evidence of severe hepatic impairment (total serum bilirubin $> 3\text{mg/dL}$), jaundice unless secondary to Gilbert's syndrome or documented liver involvement by lymphoma (see inclusion criterion 6c)

5.4.3 Definition of Female of Childbearing Potential

A sexually mature female patient or a sexually mature female partner of a male patient is considered to have childbearing potential unless she meets at least one of the following criteria:

1. Age at least 50 years and naturally amenorrhoeic for at least 24 months (i.e. has not had menses at any time in the preceding 24 consecutive months). Amenorrhoea following cancer therapy or during lactation does not rule out childbearing potential
2. Premature ovarian failure confirmed by a gynaecologist
3. Previous bilateral salpingo-oophorectomy, or hysterectomy
4. XY genotype, Turner syndrome, uterine agenesis.

5.5 Re-screening Procedures

Patients can be re-screened at the discretion of the investigator under certain circumstances. Re-screening is restricted to one attempt per patient and can only be performed if one of the following criteria is met:

- the patient has already consented and met all of the inclusion and none of the exclusion criteria and his or her enrolment was delayed due to an unexpected change in the patient's personal situation (e.g., family issues)
- the patient previously failed to be eligible due to any event (e.g., planned surgery, laboratory test result) that has been resolved
- the patient previously failed screening but has become eligible for the study based on a change in the inclusion and exclusion criteria as the result of a protocol amendment.
- the patient failed screening due to non-progressed / non-relapsed disease at the time of screening and is later clinically diagnosed as having progressed / relapsed.

A patient should only be rescreened if there is a clear indication that the patient may be eligible according to the currently valid study protocol.

In cases where previous screening activities were discontinued and enrolment did not occur, the following procedures should be implemented:

- the patient must sign and date a new informed consent form (ICF) as part of the re-screening procedure
- the eligible patient will receive a new unique identification number via the interactive response technology
- a new electronic case report form (eCRF) should be completed
- the patient will be documented as rescreened in the source documents
- all screening procedures must be completed again.

A rescreened patient can be enrolled, if all of the current inclusion criteria are met and none of the exclusion criteria are met.

6 STUDY TREATMENTS AND CONCOMITANT DRUGS

Each investigator is responsible for ensuring that deliveries of study drugs and other study materials from the sponsor and other drugs from the appropriate suppliers are correctly received, recorded, handled and stored safely and properly in accordance with all applicable regulatory guidelines, and used in accordance with this protocol. The investigator can delegate these tasks to another person (according to the local laws and regulations). Drug accountability forms will be kept by each site participating in the study and will be checked during monitoring visits.

Study drug must be handled and/or prepared as described in the Drug Preparation Manual, the IB for MOR00208, and other safety-relevant documents (e.g., Summary of Product Characteristics (SPC) for the European Medicines Agency [EMA] or the Prescribing Information [US FDA] for LEN) (see [Appendix C](#)).

6.1 MOR00208

MOR00208 will be centrally supplied. MOR00208 drug product (DP) must be stored under refrigeration at 2° C to 8° C in its original package in an appropriate storage facility accessible only to the pharmacist(s), the investigator, or a duly designated person.

MOR00208 DP is a yellowish lyophilisate supplied in single-use 20 mL glass vials. Each vial contains 200 mg of MOR00208 for reconstitution with 5 mL water for injection (WFI). Reconstitution yields 40 mg/mL MOR00208 in 25 mM sodium citrate, 200 mM trehalose and 0.02% (w/v) polysorbate 20 at pH 6.0. Each product vial is intended to deliver 200 mg of MOR00208 in 5 ml of reconstituted solution. The solution after reconstitution is colourless to slightly yellow and essentially free of foreign particles; it may contain a few white to whitish product-related particles.

For administration, MOR00208 will be diluted into a commercially available 250 mL infusion container with 0.9% (w/v) sodium chloride for injection.

MOR00208 will be administered IV at a dose of 12.0 mg/kg.

For the first 3 cycles (Cycles 1-3) of the study, each cycle will consist of a MOR00208 infusion on Day 1, Day 8, Day 15 and Day 22 of the cycle. Additionally a loading dose will be administered on Day 4 of Cycle 1. Thereafter MOR00208 will be administered on a bi-weekly (every 14 days) basis with infusions on Days 1 and 15 of each 28-day cycle.

The individual MOR00208 infusion will be prepared under aseptic conditions and administered at the study site, according to the directions of the sponsor, which will be provided in a Drug Preparation Manual. In general, a vial of MOR00208 must be used as soon as possible after reconstitution with WFI. After dilution for infusion, administration of MOR00208 should take place as soon as possible. Maximum allowed storage times and conditions will be detailed in the Drug Preparation Manual.

The preferred procedure for destruction is for all IMPs (including used, partially used, not expired unused and expired unused vials, blisters, boxes or bottles) to be returned to the Drug Depot for destruction.

In case the site is requesting formal approval for destruction of the IMP on site due to local requirements, the local destruction requirements for IMPs described in detail in the Drug Preparation Manual must be fulfilled.

For the first infusion, the IV infusion rate should be 70 mL/h for the first 30 minutes and subsequently increased to a rate of 125 mL/h; the total infusion duration should ideally not exceed 2.5 hours. All subsequent MOR00208 infusions will be administered IV at a constant rate of 125 mL/h over a 2-hour period. MOR00208 should NOT be administered as an IV push or bolus.

The infusion rate escalation schedules in this protocol and the Drug Preparation Manual are recommendations only. If required, the investigator should use clinical judgement to optimise patient safety by administering the infusion more slowly.

6.2 Lenalidomide (LEN)

Patients will self-administer a starting dose of 25 mg oral LEN daily on Days 1–21 of each cycle. Treatment with LEN may be modified in a de-escalating fashion or discontinued based upon clinical and laboratory findings. Detailed dose modification guidelines to manage haematological and/or other toxicities are provided in the respective sections of the protocol.

LEN will be obtained from a commercial source as capsules in various dose strengths for oral administration as will be outlined in the Drug Preparation Manual. If applicable, LEN will be labelled as per local regulations. Investigators must be registered through the Lenalidomide programme, as applicable in their countries (e.g., REVOLIMID REMSTM programme in the US, T-register in Germany). Patients must be counselled on the reproductive risks associated with LEN, prior to enrolment and monthly, during therapy.

6.3 Treatment with Study Drugs

Treatment consisting of **LEN** and **MOR00208** combination will be administered up to twelve 28-day cycles at specified dose levels as scheduled until disease progression, unacceptable toxicity, or discontinuation for any other reason, whichever comes first.

LEN can be given for up to 12 cycles in total. Treatment with LEN will have to be stopped after disease progression. On days when both study drugs are given together, LEN should be administered prior to MOR00208.

MOR00208 can be administered at the dose and schedule described in [Section 6.1](#) above, until disease progression, unacceptable toxicity, or discontinuation for any other reason, whichever comes first.

It is up to the investigator to decide according to the individual risk/benefit ratio if the patient should further continue on MOR00208 in case of disease progression, after discussion with the Sponsor's Medical Monitor or designee. For patients who will be administered MOR00208 despite progression of disease / relapse, an **Unscheduled Visit** including all protocol prescribed procedures for the **EOT Visit** (except the PK sample and the anti-MOR00208 antibody sample) need to be performed in order to capture the event (i.e. disease progression/relapse) for the antibody treatment to continue further ([Table 5](#)). In such cases an **EOT Visit** will take place after these patients have finally stopped receiving the antibody. And lastly, a **Safety Follow-Up** will take place **30-Days** after last administration of MOR00208.

For patients receiving antibody treatment despite disease recurrence/progression, before the administration of MOR00208, blood parameters (haematology, serum chemistry) should be evaluated in the local lab according to local guidelines/standards of local medical practice for the administration of monoclonal antibodies. A urine pregnancy test should be performed for women of childbearing potential. Vital signs should be measured according to local practice for the administration of monoclonal antibodies. For this patient population only the antineoplastic therapy after the end of study drug combination treatment and AEs need to be captured in eCRF. Other procedures described in the column "MOR00208 Additional Treatment" in [Table 5](#) will not apply for this patient population.

6.4 Pre-Medication for MOR00208 Infusions

IRRs have commonly been reported for patients with CLL or NHL treated with MOR00208.

It is suggested that the pre-medication is administered between 30 minutes and 2 hours prior to the MOR00208 infusions.

The pre-medication may include the following:

- antipyretics (e.g., acetaminophen [paracetamol] 1000 mg per dose per mouth [p.o.] or IV or equivalent)
- histamine H₁ receptor blockers (e.g., diphenhydramine 25–50 mg per dose IV or equivalent)
- histamine H₂ receptor blockers (e.g., cimetidine 300 mg p.o., ranitidine 150 mg tablet p.o. or equivalent)
- glucocorticosteroids (methylprednisolone 80–120 mg per dose IV or equivalent - please refer to [Appendix D](#))
- meperidine (25 mg per dose p.o. or IV) may be added as required for rigors or chills.

The investigator may repeat doses of individual agents as required and use other agents, doses and/or formulations in accordance with institutional guidelines. Equivalence for premedications includes variations to the stated dose due to the formulations available locally. Any premedication given should be reported in the eCRF.

Premedication for patients who do not experience any IRRs to MOR00208 during the first 3 infusions (doses) will be optional for subsequent infusions at the discretion of the investigator. Otherwise, the premedication should be continued for subsequent administrations.

6.5 Patient Monitoring During MOR00208 Infusion

Vital signs should be measured as outlined in [Section 7.2.8](#). All supportive measures consistent with optimal patient care will be provided throughout the study according to institution standards.

Precautions for anaphylaxis should be observed during MOR00208 administration. Emergency resuscitation equipment and medications should be readily available. Additional supportive measures should also be available and may include, but are not limited to, epinephrine, antihistamines, corticosteroids, IV fluids, vasopressors, oxygen, bronchodilators, diphenhydramine, and acetaminophen (paracetamol).

6.6 Criteria for Dose Modifications and Drug Discontinuation

6.6.1 Management of MOR00208 Infusion-Related Reactions (IRRs)

IRRs will be defined according to the National Cancer Institute Common Terminology Criteria for Adverse Events (NCI-CTCAE), Version 4.0 definition of IRR and cytokine release syndrome ([Table 1](#)).

**Table 1 Definition of Infusion-Related Reaction
 NCI-CTCAE Version 4.0, Selection Criteria: Infusion-Related Reaction and Cytokine Release Syndrome**

Adverse Event	Grade 1	Grade 2	Grade 3	Grade 4
IRR	Mild transient reaction; infusion interruption not indicated; intervention not indicated	Therapy or infusion interruption indicated but responds promptly to symptomatic treatment (e.g., antihistamines, NSAIDS, narcotics, IV fluids); prophylactic medications indicated for ≤ 24 hours	Prolonged (i.e. not rapidly responsive to symptomatic medication, brief interruption of infusion, or both); recurrence of symptoms following initial improvement; hospitalisation indicated for clinical sequelae	Life-threatening consequences; urgent intervention indicated
Cytokine release syndrome	Mild reaction; infusion interruption not indicated; intervention not indicated	Therapy or infusion interruption indicated but responds promptly to symptomatic treatment (e.g., antihistamines, NSAIDS, narcotics, IV fluids); prophylactic medications indicated for ≤ 24 hours	Prolonged (i.e. not rapidly responsive to symptomatic medication and/or brief interruption of infusion); recurrence of symptoms following initial improvement; hospitalisation indicated for other clinical sequelae (e.g., renal impairment, pulmonary infiltrates)	Life-threatening; consequences; pressor or ventilatory support indicated

Abbreviations: IRR=infusion-related reaction; IV=intravenous; NSAIDs=non-steroidal anti-inflammatories.

Please note: An acute infusion reaction may occur with an agent that causes cytokine release (e.g., monoclonal antibodies or other biological agents). Signs and symptoms usually develop during or shortly after drug infusion and generally resolve completely within 24 hours of completion of infusion. Signs/symptoms may include: Allergic reaction/hypersensitivity (including drug fever); Arthralgia (joint pain); Bronchospasm; Cough; Dizziness; Dyspnoea (shortness of breath); Fatigue (asthenia, lethargy, malaise); Headache; Hypertension; Hypotension; Myalgia (muscle pain); Nausea; Pruritis/itching; Rash/desquamation; Rigors/chills; Sweating (diaphoresis); Tachycardia; Tumour pain (onset or exacerbation of tumour pain due to treatment); Urticaria (hives, welts, wheals); Vomiting

6.6.1.1 Grade 2 IRRs

If a patient presents with a grade 2 infusion reaction:

- the infusion should be stopped immediately
- the patient should receive appropriate further treatment with an antihistamine and/or acetaminophen (paracetamol) or methylprednisolone (or equivalent) if clinically indicated
- once the symptoms have been resolved or reduced to “mild” according to investigator assessment, the infusion can be continued at an infusion rate of 50%. If, after one hour, the patient’s symptoms do not return and vital signs are stable, the infusion rate may be increased every 30 minutes, as tolerated, to the baseline rate.

If a patient who developed a grade 1 or 2 IRR receives further infusions, then premedication should be given before all subsequent infusions of MOR00208.

6.6.1.2 Grade 3 IRRs

If a patient presents with a grade 3 IRR:

- the infusion should be stopped immediately
- the patient **must** receive appropriate treatment with an antihistamine and/or acetaminophen (paracetamol) or methylprednisolone (or equivalent) and, if necessary, further medications (i.e. epinephrine, bronchodilator)
- a blood sample for cytokine analysis should be obtained during the event and approximately 24 hours later
- only after the complete resolution of all symptoms (to \leq grade 1), and after having received appropriate prophylactic medication(s) as described above, the infusion may be resumed at an infusion rate of 25%. If, after 1 hour, the patient’s symptoms do not return and vital signs are stable, the infusion rate may be increased to a maximum of 50%
- if, after the resumption of the infusion, symptoms return (irrespective of grade), the infusion must be stopped immediately and the infusion tubing should be disconnected from the patient.

Based on the investigator’s decision the patient may receive further MOR00208 provided clinically appropriate precautions were undertaken. The patient may continue treatment with LEN.

6.6.1.3 Grade 4 IRRs

If a patient presents with a grade 4 IRR:

- the infusion should be stopped immediately and the infusion tubing should be disconnected from the patient
- the patient should receive appropriate treatment with an antihistamine and/or acetaminophen (paracetamol) or methylprednisolone (or equivalent) and, if necessary, further medications (i.e. epinephrine, bronchodilator)
- a blood sample for cytokine analysis should be obtained during the event and approximately 24 hours later.

The patient must not receive further MOR00208, but may continue treatment with LEN as per protocol.

6.6.2 Management of Toxicities

The next cycle of treatment may begin on the scheduled Day 1 if:

- ANC is $\geq 1.000/\text{mm}^3$ (unless neutropenia is due to infiltration of bone marrow)
- Platelets $\geq 50000/\text{mm}^3$ (unless thrombocytopenia is due to infiltration of bone marrow, patient may have received transfusion) and absence of active bleeding
- No serious organ or other toxicity present.

If, based on medical judgment, the treating physician considers a change in laboratory parameter or AE not to be a study drug-related toxicity, but to represent a natural fluctuation in or progression of the underlying disease, then it is at the physician's discretion and assessment of the individual risk/benefit ratio to determine whether the patient should be dosed. The decision and rationale behind the decision should be documented in the source data.

If the above conditions are not met on Day 1 of a new cycle, the subject will be evaluated once every seven days and a new cycle will not be initiated until the toxicity has resolved as described above. Specific course of action for a given toxicity occurring in the course of the treatment cycle is described below.

If treatment needs to be interrupted for ≤ 28 days for the same study drug-related toxicity, the patient's treatment should continue, depending on the duration of treatment interruption, at the next protocol scheduled visit. No missed visits or doses of either drug should be made up.

If treatment with one study drug needs to be interrupted for >28 days for the same, persistent, drug-related toxicity, the study drug judged by the investigator to have caused the toxicity should be discontinued and the patient should continue to be dosed with the other study drug, as per protocol.

If treatment with both study drugs needs to be interrupted for >28 days for the same persistent study drug-related toxicity, judged by the investigator to be related to both study drugs (LEN and MOR00208), then the End of Treatment Visit will be performed and the patient will enter the follow-up phase (see [Section 5.3.1](#)).

6.6.2.1 Haematological and Other Toxicities

Subjects will be evaluated for AEs at each visit with the NCI CTCAE v4.0 used as a guide for grading severity. The dose of study drug(s) for each patient will be interrupted and/or modified following toxicity as described below. Refer to [Table 2](#) and [Table 3](#) for instructions on dosing interruptions/modifications and [Table 4](#) for LEN dose reduction instructions.

Guidance on managing specific toxicities is summarised in [Table 2](#) and [Table 3](#).

Table 2 Haematological and Other Toxicities

Grade 3/4 thrombocytopenia judged to be related to study drugs	PLTs fall to <50000/ μ l	Interrupt MOR00208* and LEN dosing) Follow CBC every 7 days
	PLTs return to \geq 50000/ μ l	Provided all other criteria are fulfilled, resume dosing of MOR00208 and/or LEN. LEN should be administered at the next lower dose level (Table 4)
Grade 3/4 neutropenia judged to be related to study drugs	ANC falls to <1000/ μ l for at least 7 days or ANC falls to <1000/ μ l with an associated body temperature \geq 38.5°C or ANC falls to <500/ μ l	Interrupt MOR00208* and LEN dosing Follow CBC every 7 days Growth factors (G-CSF) and antimicrobial prophylaxis is to be used, as per local guidelines
	ANC return to \geq 1000/ μ l	Provided all other criteria are fulfilled, resume dosing of MOR00208 and/or LEN. LEN should be administered at the next lower dose level (Table 4)
Other clinically significant toxicities judged to be related to study drugs	Grade 3/4	Interrupt the administration of the study drug(s)* to which the toxicity is judged to be related to.
	Toxicities resolve to grade \leq 2	Provided all other criteria are fulfilled, resume dosing of study drug(s). LEN should be administered at the next lower dose level (Table 4)

Abbreviations: ANC=absolute neutrophil count; CBC=complete blood count; G-CSF=granulocyte colony-stimulating factor; LEN=lenalidomide; PLT=platelets.

*If, based on medical judgment, the treating physician considers a laboratory parameter change or AE not to be a study drug-related toxicity, but to represent a natural fluctuation in or progression of the underlying disease, then it is at the physician's discretion and assessment of the individual risk/benefit ratio to determine whether the patient should be dosed. The decision and rationale behind the decision should be documented in the source data.

Table 3 Other Toxicities Judged to be Related to LEN

Thromboembolic events	Grade 3/4	Interrupt LEN dosing Start anticoagulation as per local guidelines Continue MOR00208 treatment as per protocol
	Toxicities resolve to grade \leq	Restart LEN at investigator's discretion (maintain dose level) Continue MOR00208 treatment as per protocol
Allergic reaction or hypersensitivity grade 3/4 (including but not limited to Stevens-Johnson syndrome, toxic epidermal necrolysis, exfoliative or bullous rash, angioedema)	Grade 3/4	Discontinue LEN permanently Continue MOR00208 treatment as per protocol
Allergic reaction or hypersensitivity	Grade >2	Interrupt LEN dosing Follow at least every 7 days Continue MOR00208 treatment as per protocol
	Resolved to \leq grade 2 severity or at least the baseline value (for pre-existing conditions; at screening)	Restart LEN (next lower dose level)
Desquamating (blistering) rash \geq grade 3 or nondesquamating rash grade 4 considered to be related to LEN		Discontinue LEN permanently Continue MOR00208 treatment as per protocol
Nondesquamating rash	Grade 3/4	Interrupt LEN dosing Continue treatment with MOR00208 as per protocol
	Resolve to grade \leq 1	Restart LEN at next lower dose level
Tumour flare reaction	Grade 3/4	Interrupt LEN dosing Provide symptomatic treatment as per local guidelines Continue treatment with MOR00208 as per protocol

	Resolve to grade \leq 1	Restart LEN (maintain same dose level)
Tumour flare reaction	Grade 1/2	Provide symptomatic treatment as per local guidelines Continue LEN without dose modification or interrupt LEN dosing at investigator's discretion Continue treatment with MOR00208 as per protocol

Abbreviation: LEN=lenalidomide.

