For the first 3 cycles (Cycles 1-3) of the study each cycle will consist of a MOR00208 infusion on Day 1, Day 8, Day 15 and Day 22 of the cycle. Additionally a loading dose will be administered on Day 4 of Cycle 1. Thereafter MOR00208 will be administered on a bi-weekly (every 14 days) basis with infusions on Day 1 and Day 15 of each 28-day cycle.

MOR00208 can be administered until disease progression, or unacceptable toxicity or discontinuation for any other reason, whichever comes first. It is up to the investigator to decide, according to the individual risk/benefit ratio, if the patient should continue on MOR00208 in spite of disease progression (refer to [Section 7.2.3](#)).

LEN:

Patients will self-administer a starting dose of 25 mg oral LEN daily on Days 1–21 of each cycle. Treatment with LEN may be modified in a de-escalating fashion or discontinued based upon clinical and laboratory findings. Detailed dose modification guidelines to manage haematologic and/or other toxicities are provided in the respective sections of the protocol.

LEN can be given for up to 12 cycles in total.

Treatment with LEN will have to be stopped in case of disease progression, or unacceptable toxicity, or discontinuation for any other reason, whichever comes first.

Objective disease response assessments will be made according to the revised response criteria based on the guidelines of the International Working Group (IWG) reported by [Cheson et al. \(2007\)](#). The data used for the primary statistical analyses will be derived from a central

independent review of the radiological + clinical disease assessments. A charter outlining the central imaging plus clinical assessment will be prepared.

Approximately 80 patients with R-R DLBCL who meet the inclusion criteria and have none of the exclusion criteria will be enrolled in the study. This study will be conducted under a United States (US) Food and Drug Administration (FDA) Investigational New Drug (IND) application.

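### Protocol Table 3 tells sites both to stop lenalidomide for good and to restart it one level lower after a lenalidomide-related grade 4 nondesquamating rash

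*Protocol*

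**What the plan says.** Protocol section 6.6.2.1 refers sites to Tables 2 and 3 for dose interruptions and modifications, and to Table 4 for the LEN dose levels. Table 3 is headed "Other Toxicities Judged to be Related to LEN". Two adjacent entries deal with rash:

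- **Stop row.** The trigger is desquamating rash of grade 3 or higher, or "nondesquamating rash grade 4 considered to be related to LEN". The action is "Discontinue LEN permanently Continue MOR00208 treatment as per protocol".
- **Restart row.** The trigger is nondesquamating rash, grade 3/4. The action at onset is "Interrupt LEN dosing Continue treatment with MOR00208 as per protocol". On resolution to grade 1 or less, the action is "Restart LEN at next lower dose level".

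Three general rules also bear on the point. Under section 6.6.2, after an interruption of 28 days or less for the same drug-related toxicity, "treatment should continue, depending on the duration of treatment interruption, at the next protocol scheduled visit"; beyond 28 days the responsible drug is discontinued. Section 5.1.2 says: "Treatment with LEN will have to be stopped in case of disease progression, or unacceptable toxicity, or discontinuation for any other reason". It also says: "LEN can be given for up to 12 cycles in total".

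**The concern.** A LEN-related nondesquamating rash of grade 4 satisfies both triggers. Once it has resolved, one row forbids LEN and the other directs a restart. Two sites could handle the same event in opposite ways, each following a row of the table.

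Protocol section 8.1 defines grade 4 as life-threatening, so the unclear rule is about giving the drug again after a life-threatening reaction attributed to it. This is a matter of patient safety and consistent dosing. It does not touch the estimand, the sample size or the primary analysis of objective response.

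**Working it through.** The plan states no figure to reproduce. The check is a comparison of the rows, a search for a rule that reconciles them, and some arithmetic on Table 4 to show what is at stake.

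**1. Each rash type and grade against the rows of Table 3**

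| LEN-related rash | Stop row | Restart row | Instructions |
|---|---|---|---|
| Desquamating, grade 3 | applies | – | 1 |
| Desquamating, grade 4 | applies | – | 1 |
| Nondesquamating, grade 3 | – | applies | 1 |
| Nondesquamating, grade 4 | applies | applies | 2 |

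One of the four combinations carries two instructions. The rows agree at onset (LEN is stopped, MOR00208 continues) and part only after resolution.

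**2. Does anything separate the rows?**

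- *Relatedness.* The stop row specifies a relation to LEN, but the table heading already limits every row to LEN-related toxicity.
- *The 28-day rule (section 6.6.2).* It ends LEN only after more than 28 days of interruption. For a rash that resolves sooner it says treatment should continue, which does not settle the matter.
- *Unacceptable toxicity (section 5.1.2) and the withdrawal criteria (section 6.9.1).* Neither is tied to a rash grade, and neither picks a row.
- *Section 6.6.2.2.* It sets the one-level reduction steps and states no precedence between rows.
- *SmPC or Prescribing Information.* Section 6.6.2.2 points to these for current LEN dosing information, and they are supplied to sites (section 6, Appendix C). They are not available here, so whether they settle the point is unknown.
- *SAP.* It contains no dosing rule for rash.

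**3. Dose difference for a full cycle after restart**

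Formula: next lower dose level (Table 4) × 21 dosing days, against 0 mg under the stop row.

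| Dose before the event | Restart dose | LEN per cycle, restart row | Stop row |
|---|---|---|---|
| 25 mg | 20 mg | 20 × 21 = 420 mg | 0 mg |
| 20 mg | 15 mg | 15 × 21 = 315 mg | 0 mg |
| 15 mg | 10 mg | 10 × 21 = 210 mg | 0 mg |
| 10 mg | 5 mg | 5 × 21 = 105 mg | 0 mg |
| 5 mg | none | – | 0 mg |

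The conflict can therefore arise at 4 of the 5 dose levels. These figures describe exposure, not clinical effect.

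**4. How many patients could this version still affect?**

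LEN is limited to 12 cycles, nominally 12 × 28 = 336 days; delayed cycles can lengthen that. SAP section 8.2 lists a LEN completion entry dated 20 August 2017. This protocol version is dated 24 February 2021, which is 1,284 days later (1,096 days to 20 August 2020, plus 188). It is likely that few or no patients were still on LEN. This is an inference, because the documents give no date of last enrolment.

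**The case against.** The best answer is that an ordinary reading resolves the conflict. The stop row names grade 4 alone for this rash, the other row is broader, and a permanent stop leaves nothing to restart. The grade 3/4 allergic-reaction row, which includes exfoliative and bullous rash, also orders a permanent stop, so the table leans that way. That is the sensible reading, and the fix below adopts it. But the restart row also names grade 4 in terms, and the protocol states no rule that the narrower row prevails.

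There are real safeguards. LEN stops at onset under either row, and restart waits for grade 1 or less, which leaves time to use the round-the-clock medical contact in section 8.2. A new cycle may not begin while serious toxicity persists (section 6.6.2). A grade 4 event would normally be reported as serious within 24 hours (sections 8.1 and 8.2), and the investigator may withdraw a patient for any adverse event (section 6.9.1). These lower the risk, but none says which row governs a restart within 28 days.

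It is also fair to say that this is a drafting contradiction and not a deliberate design choice, that the milligram figures only multiply out the dose table, and that correcting this version may change no patient's care. All of that stands and keeps the point small. It does not remove the overlap.

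**Conclusion.** The concern holds, as a minor one. For LEN-related grade 4 nondesquamating rash, Table 3 gives two instructions that cannot both be followed once the rash has resolved, and nothing in the protocol or SAP ranks them. The conflict is confined to one of four rash type-and-grade combinations. It applies where the interruption lasts 28 days or less and the patient was above 5 mg. The exposure difference runs from 105 to 420 mg per full cycle, against none.

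The number of patients is unknown and probably few or none under this version. The conclusion rests on the table's text as printed and would not change if the LEN label proved to be clear, since the protocol's own table would still contradict itself.

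**What to change.** Change the trigger of the nondesquamating-rash interrupt-and-restart row from grade 3/4 to grade 3. The stop row then governs grade 4 alone, and none of the four combinations carries two instructions.

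- If no patient is still on LEN, make the correction in any protocol that reuses the table.
- If a patient is still on LEN, also notify the sites.
- In the study report, list any grade 4 nondesquamating rash and whether LEN was restarted. The planned adverse-event listing (SAP 10.7.3.1.2) and the LEN dosing-record listing (SAP 8.9.6) already hold the data.

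The cost is one table cell and a short note in the report, plus a site letter only if someone is still being dosed. The possible downside is a few more permanent LEN discontinuations.

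One separate check, which is not part of this finding: as printed, the allergic-reaction row that permits restart is triggered above grade 2 and so overlaps the grade 3/4 permanent-stop row. That turns on a single symbol. The sponsor should confirm it against the source table and, if it is right, remove that overlap too, so that grade 3/4 reactions follow only the permanent stop.
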